[name]. [name]
Klinik für Nephrologie und Rheumatologie
Universitätsmedizin Göttingen
[name]
[name]
Tel. (office): [contact]
Fax (office): [contact]
E-Mail: [contact]

Private address:

[name]. [name]

Tel. [REDACTED]

4 Table of Contents

1	Study Title: European Alport Therapy Registry- EARLY PRO-TECT Alport XXL	1
2	Approval Signature Page	2
3	Organisational Structure	3
4	Table of Contents.....	5
5	Synopsis	6

5 Synopsis

Study Title	European Alport Therapy Registry- EARLY PRO-TECT Alport XXL
Type of Project	Non-interventional, observational prospective (and in parts retrospective) study in oligosymptomatic children with Alport syndrome
Sponsor	Georg-August-Universität Göttingen Stiftung Öffentlichen Rechts Universitätsmedizin Göttingen Vorstand [name] [name] [contact] [contact]
Coordinating Principal Investigator	[name]. [name] Klinik für Nephrologie und Rheumatologie Universitätsmedizin Göttingen [name] [name] [contact] [contact] Email: [contact]
Deputy for Coordinating Principal Investigator	[name] Klinik für Nephrologie und Rheumatologie Universitätsmedizin Göttingen [name] [name] [contact] [contact] Email: [contact]
(Sub-) Investigators	A list of sub-investigators participating in this study is kept at the Trial Office (UMG, Göttingen)
Participating Trial Sites	A list of investigators and trial sites participating in this study are kept on file at the Trial Office (UMG, Göttingen).
Hypothesis	Treatment of Alport syndrome with Renin–angiotensin–aldosterone system inhibition from early stages of disease is safe and slows disease progression.
Rationale	The type IV collagen disease Alport syndrome is the second most common monogenic cause of end-stage renal failure. Children with Alport syndrome develop renal failure early in life. Renin–angiotensin–aldosterone system (RAAS) inhibition is the first-line off-label therapy

	
for proteinuric children with Alport syndrome and can delay renal failure in a time dependent manner.
 
The EARLY PRO-TECT Alport trial was the first randomized and placebo-controlled trial to evaluate safety and efficacy of RAAS-inhibition in children with Alport syndrome. The trial indicated safety and efficacy of nephroprotective therapy without statistical significance. Aim of this planned study is to analyse renal outcome and adverse effects in the longterm observation of all children of the trial to further increase quality of the original trial results.
 
Adult patients with Alport syndrome suffer from progressive sensorineural hearing loss and eye abnormalities are often found. The development and characteristics of hearing loss and the prevalence of ocular findings in children with Alport syndrome need to be further analyzed. This study also aims to further characterize hearing loss and ocular findings in AS.
	
Study Medication	Non-interventional observational trial	
Placebo	Non-interventional observational trial	
Study Design	Strictly observational, non-interventional data acquisition with prospective (and in parts retrospective) data analysis	
EARLY PRO-TECT Alport XXL		

 
 
estimated 66 children/ young adults who participated in EARLY PRO-TECT Alport trial
 
 
 
estimated 250 children/ young adults in disease stages 0, I, or II from China, Germany, Japan, South Korea, UK, USA and other countries
 
 
		

 
all participants must fulfill criteria for definitive genetic diagnosis
 
Retrospective data collection of
 
Medical history with focus on disease progression and treatment
 
		
Baseline		

 
Prospective data collection of kidney outcome measures and adverse events
 
		
Study Termination 2024		

 
Evidence synthesis for efficacy and safety of nephroprotective therapy in young patients living with Alport syndrome
 
		

	
Pseudonymized follow-up of the 66 children from the EARLY PRO-TECT Alport trial (with the exception of drop-out patients) as well as inclusion and follow-up of children with Alport syndrome in disease stages 0,I,II (i.e. comparable to the patient group of the EARLY PRO-TECT Alport trial) from South Korea, USA, Canada, China, France, England, Spain and Germany
 
Alport Syndrome disease stages are defined as:
 
 
0	Microhaematuria without microalbuminuria	
 
I	Microalbuminuria (30-300 mg albumin/gCrea)	
 
II	Proteinuria >300 mg albumin/gCrea	
 
III	>25% decline of normal creatinine clearance	
 
IV	End stage renal failure (ESRF)	
 
 
Information on kidney function of the children will be collected as available from existing routine records. Adverse events (hyperkalemia, cough, hypotension, ANV, malignancy, death) will be monitored. Pseudonymized additional data regarding hearing function, ocular findings and genetic results will be obtained by medical reports as available.
	0	Microhaematuria without microalbuminuria	I	Microalbuminuria (30-300 mg albumin/gCrea)	II	Proteinuria >300 mg albumin/gCrea	III	>25% decline of normal creatinine clearance	IV	End stage renal failure (ESRF)
0	Microhaematuria without microalbuminuria										
I	Microalbuminuria (30-300 mg albumin/gCrea)										
II	Proteinuria >300 mg albumin/gCrea										
III	>25% decline of normal creatinine clearance										
IV	End stage renal failure (ESRF)										
Timetable	
Date of study / recruitment Start May 2021
 
Date of termination of recruitment May 2022
 
Date of study termination May 2024
										
Total Number of Patients	Total: 90-250										
Study population	Oligosymptomatic children and young adults with Alport syndrome in early disease stages										
Inclusion Criteria	
 1. Definitive diagnosis of Alport syndrome by kidney biopsy (patient or affected relative/s), and/or genetic analysis 2. Alport syndrome stages 0, I or II at baseline, if the patient did not participate in EARLY PRO-TECT ALPORT trial 3. Patient expresses willingness to participate in observational study 										
Exclusion Criteria	
 1. uncertain Alport diagnosis 2. Alport syndrome stages III or IV at baseline, if the patient did not participated in EARLY PRO-TECT ALPORT trial 3. Patient expresses unwillingness to participate in observational study 										

Documentation Schedule	Baseline document (at baseline) and follow up document (at every consultation)
Study Objectives	
Study Objectives: Aim of this planned study is to analyse renal outcome and adverse events in the longterm observation of oligosymptomatic children with Alport syndrome, who participated in the EARLY PRO-TECT ALPORT trial. Treated and untreated children in similar disease stages will be included from South Korea, Germany, UK, France, Spain, USA, Canada and China to further increase evidence and to enable a comparison between treated and untreated children.
 
Study Endpoints: Primary Endpoint: time to progress of Alport Syndrome to the next disease stage under treatment
 
Stage 0 to I : Albuminuria >30 mg albumin/gCrea in combination with a 3-fold increase from baseline in albuminuria
 
Stage I to II: Albuminuria >300 mg albumin/gCrea or two-fold increase from baseline albuminuria
 
Stage II to III: Two-fold increase from baseline albuminuria
 
Secondary Endpoint: Time to progress of Alport Syndrome to the next disease stage under treatment compared to children without treatment
 
Further exploratory endpoints will be assessed during this study if data warrant and include, e.g., percentage of patients with disease progression.
 
For future evaluation for upcoming new therapies or for earlier diagnosis or for therapeutic response to therapy bio-material (urine and serum) of individual patients will be stored at the University Medical Center in Goettingen.

Safety	Safety is assessed by recording of adverse events and laboratory parameters.
Data-Safety	All data will be collected in pseudomized form at the trial site in Goettingen. All electronic data will be stored on the internal server of the University Medical Center Goettingen (intranet). Only the local team of the principal investigator will have access to the data with their

	individual personal account (access to be granted by the principal investigator).
Statistical Analysis	Statistical analysis of this study will be the responsibility of the Dept. Medical Statistics, Universitätsmedizin Göttingen, Georg-August-Universität. The primary endpoint 'time to progress of Alport syndrome will be assessed. If indicated, additional potentially confounding variables such as age will be added to the model.
Pharmacological-toxicological Evaluation	Not applicable
Risks, Adverse Drug Reactions, Drug Interactions, Restrictions, Contraindications, Procedures in Case of Emergency	Not applicable
Risk-benefit Analysis	Not applicable

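### The stage limit for non-trial children is applied at registry entry, so children already on treatment are admitted only if they have not yet reached stage III or IV

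*Protocol*

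**What the plan says.** All places are in the Protocol, section 5 (Synopsis).

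- **Hypothesis:** "Treatment of Alport syndrome with Renin–angiotensin–aldosterone system inhibition from early stages of disease is safe and slows disease progression".
- **Inclusion criterion 2:** "Alport syndrome stages 0, I or II at baseline, if the patient did not participate in EARLY PRO-TECT ALPORT trial".
- **Exclusion criterion 2:** "Alport syndrome stages III or IV at baseline, if the patient did not participated in EARLY PRO-TECT ALPORT trial". Former trial participants are thus exempt from both stage rules.
- **Study Design, flow chart:** above the baseline line stands retrospective collection of "Medical history with focus on disease progression and treatment"; below it stands "Prospective data collection of kidney outcome measures and adverse events".
- **Study Objectives:** "Treated and untreated children in similar disease stages will be included". Nothing requires treatment to begin at or after entry.
- **Primary endpoint:** "time to progress of Alport Syndrome to the next disease stage under treatment". The secondary endpoint compares this time with that of untreated children. No time origin is stated for either.
- **Stage definitions:** stage III is a loss of more than 25% of normal creatinine clearance; stage IV is end-stage renal failure.

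**The concern.** The hypothesis is about treatment begun in an early stage. The stage rule looks at the child's stage when joining the registry, which may be years later.

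Take two non-trial children who start RAAS inhibition in stage II on the same day, some years before recruitment opens. One has reached stage III by entry and is excluded. The other is still in stage II and enters as a treated child with early disease. Entry therefore depends partly on how the disease went on treatment. This is prevalent-user selection.

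At stake is the time to progression reported for treated non-trial children, who would be a slower-progressing remnant of those who started. The former trial participants, with whom they are studied, are not filtered in this way. Adjusting for age or other covariates cannot bring back children who were never admitted.

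**Working it through.** **What baseline means.** The protocol does not define it in words. Three places point to registry entry: the flow chart order (history, baseline, prospective collection), the documentation schedule (one form at baseline, then one at each consultation), and the absence of any link to treatment start.

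**Whom the rule removes.** Exclusion 2 is set beside the endpoint definitions:

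| Course before entry (non-trial child) | Endpoint event? | Barred from entry? |
|---|---|---|
| Stage 0 to I (if endpoint thresholds are met) | Yes | No |
| Stage I to II | Yes | No |
| Albuminuria doubles, still stage II | Yes (used as II to III) | No |
| Clearance loss above 25%, or end-stage failure | Not itself the listed criterion | Yes |

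Selection therefore acts on stage III or IV only. It bears mainly on children who started treatment in stage II, one step from the limit.

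**How this affects the estimate.** There is no plan figure to reproduce. The illustration below takes stage II starters and counts reaching stage III as the event.

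Inputs:
- From the protocol: follow-up F = 3 years at most (May 2021 to May 2024).
- Assumed: hazard h of reaching stage III on treatment = 0.05, 0.10 or 0.15 per year.
- Assumed: time on treatment before entry L = 2, 4 or 6 years.
- Assumed: hazards either equal in all children, or varying by a gamma frailty with mean 1 and variance 1.

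*Share excluded.* Equal hazards: 1 − exp(−hL). Frailty: 1 − 1/(1 + hL).
- Lowest (h = 0.05, L = 2, frailty): 1 − 1/1.10 = 9%.
- Highest (h = 0.15, L = 6, equal): 1 − exp(−0.90) = 59%.

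*Clock from treatment start, no delayed entry.* With equal hazards, events per admitted child are 1 − exp(−hF), and person-years are L + [1 − exp(−hF)]/h. For h = 0.10 and L = 4: 0.259/(4 + 2.592) = 0.039 per year, which is 0.39 of the true 0.10. The L years before entry are event-free by selection but are counted as time at risk. Over the whole grid, frailty included, the ratio to the true rate over the same span is 0.22 to 0.58.

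*Clock from registry entry.* With equal hazards the rate is h and the ratio is 1.00: no bias. With frailty, per admitted child:
- events = 1 − (1 + hL)/(1 + h(L + F))
- person-years = [(1 + hL)/h] × ln[(1 + h(L + F))/(1 + hL)]

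For h = 0.10 and L = 4: events 1 − 1.4/1.7 = 0.176; person-years 14 × ln(1.7/1.4) = 2.718; rate 0.065. New starters over their first 3 years: (1 − 1/1.3)/(10 × ln 1.3) = 0.231/2.624 = 0.088. The ratio is 0.74. Over the grid it is 0.57 to 0.91.

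The conclusion therefore depends on the time origin and on how much children's hazards differ. The protocol supplies neither.

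**The case against.** **Most treatment failures can still enter.** A reader might infer that the treated group consists of children in whom treatment has not failed. The documents do not support that: three of the four courses in the table above leave a child eligible. This stands, and it limits the point to stage III and IV.

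**The filter is not aimed at treated children.** It removes fast-progressing untreated children too. A reader might infer a bias in favour of treatment in the secondary endpoint. The net direction depends on how long each group was at risk before entry, which the documents do not say. This stands.

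**Harm.** A reader might infer that adverse events will look rarer. The rule does not select on adverse events or on stopping treatment, so this does not follow.

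**The clock belongs to the SAP.** Time origin and delayed entry are commonly set there, and the SAP is not at hand. This is fair for the analysis. It does not answer the eligibility point, because no analysis can use children who were not admitted.

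**The rule serves comparability.** Admitting only stages 0 to II is meant to match the trial population. But former trial participants are kept whatever their stage now, so the match is to stage at trial entry. A rule based on present stage does not reproduce it.

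**A one-sided remedy would do harm.** Moving the stage test to treatment start for treated children alone would admit treated but not untreated children now in stage III. This is correct, so the remedy must apply to both groups.

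**Conclusion.** The point holds in a limited form. If baseline is registry entry, non-trial children who reached stage III or IV earlier are removed, and those who enter already on RAAS inhibition are selected for slower progression, chiefly among stage II starters. Former trial participants are not selected in this way.

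With time from treatment start and no delayed entry, progression under treatment is understated. With time from registry entry, it is understated only to the extent that hazards differ between children, and hardly at all if they are alike.

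No size can be given from the documents. The ranges in the working rest on assumed hazards, treatment durations and frailty. They describe reaching stage III as the protocol defines it, whereas the endpoint for stage II is a doubling of albuminuria, so they carry over only as far as the two go together. The share of non-trial children already on treatment at entry is also not given. The improvement is nevertheless cheap and worth making.

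**What to change.** **Preferred.** Apply inclusion 2 and exclusion 2 to all non-trial children from the retrospective history: the stage documented at treatment start for treated children, and at the first documented staging for untreated children, whatever the present stage. This gives both groups the treatment that former trial participants already have. State in words what baseline means.

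**If recruitment has closed or the rule stays at registry entry:**
- record the treatment start date and treatment duration at entry;
- count time from treatment start, with delayed entry at baseline;
- report the primary and secondary endpoints separately for children who start treatment at or after baseline and for prevalent users;
- limit the conclusion for non-trial prevalent users to children who had not reached stage III or IV by entry.

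**Cost.** A change of protocol wording, use of history already planned for collection, and somewhat more analysis. Children without a documented earlier stage move to a supportive set. The new-starter subgroup may be small: recruitment runs for one year, and the planned total is 90 to 250. It should therefore stand beside the full treated set and not replace it as the only main analysis.

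### Progression from stage I and stage II is defined without a confirming albuminuria value and assessed at unscheduled visits, so stable children can be counted as progressed, more often the more they are seen

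*Protocol*

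**What the plan says.** The protocol's Synopsis (section 5, Study Objectives row) makes the primary endpoint "time to progress of Alport Syndrome to the next disease stage under treatment". It then gives one event rule per starting stage:

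- For children starting in stage 0, two conditions must hold together: "Stage 0 to I : Albuminuria >30 mg albumin/gCrea in combination with a 3-fold increase from baseline in albuminuria".
- For children starting in stage I, either of two conditions is enough: "Stage I to II: Albuminuria >300 mg albumin/gCrea or two-fold increase from baseline albuminuria".
- For children starting in stage II, there is one condition only: "Stage II to III: Two-fold increase from baseline albuminuria".

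None of the three says whether a second value must also meet the criterion. The Documentation Schedule row reads "Baseline document (at baseline) and follow up document (at every consultation"), with no interval or number of visits. Under Study Design, kidney data are "collected as available from existing routine records". The secondary endpoint uses the same event to compare treated with untreated children. The Timetable closes recruitment in May 2022 and the study in May 2024.

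**The concern.** In a time-to-event analysis the first qualifying value ends a child's event-free time. If one value is enough, every consultation is another chance for measurement variation to produce an event, and all these chances are judged against the same baseline value. A child whose true albuminuria never changes can then be counted as progressed. The probability depends on how often routine care happens to measure that child.

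Two results are at stake. Time to progression in the primary analysis would be too short for children starting in stage I or II. In the secondary analysis, whichever group is seen more often would appear to progress faster, whatever treatment does. The first limb of the stage I rule is the most exposed: it needs no fold-rise, so a stable child a little below 300 mg/g can cross it on variation alone.

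**Working it through.** The protocol states no event rate, power calculation or misclassification rate, so there is no figure of its own to reproduce.

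**Inputs from the protocol.** The three event rules; the stage I range of 30 to 300 mg/g; prospective follow-up of 2 years (May 2022 to May 2024) to 3 years (May 2021 to May 2024).

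**Assumptions, because the protocol gives no values.** Each child's true level is constant. Errors are independent and log-normal, with within-child SD s = 0.2 to 0.5 on the log scale. There is one baseline value and k follow-up values, with k = 8 as the main case (4 a year over 2 years, or 8/3 = about 2.7 a year over 3 years). A two-fold increase means at least twice baseline.

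**Step 1: one consultation, doubling rule.** The difference of two log values has SD s√2, so the chance of a spurious doubling is 1 − Φ(ln 2 / (s√2)). For s = 0.3 this is 1 − Φ(0.693/0.424) = 1 − Φ(1.63), or 5.1%. For s = 0.2, 0.4 and 0.5 it is 0.7%, 11% and 16%.

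**Step 2: k consultations sharing one baseline.** The chance of at least one spurious doubling is 1 − E[Φ(ln 2 / s + Z)^k], with Z a standard normal variable for the baseline error. Simulation of stable children gives the same 8-visit figures and supplies the last column, where two consecutive values must qualify.

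| s | k = 4 | k = 8 | k = 12 | k = 8, confirmed |
|---|---|---|---|---|
| 0.2 | 2% | 4% | 6% | 0.4% |
| 0.3 | 15% | 22% | 27% | 5% |
| 0.4 | 28% | 39% | 46% | 13% |
| 0.5 | 38% | 51% | 58% | 20% |

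This is the stage II rule.

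**Step 3: stage I rule, k = 8,** keeping children whose observed baseline lies in 30 to 300 mg/g. At a true 100 mg/g the shares are almost those of the table. At a true 200 mg/g they are 18% to 79% for s = 0.2 to 0.4, and about 1% to 24% with confirmation. At a true 250 mg/g, near the top of the range, they are 80% to 96%, and 19% to 51% with confirmation.

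**Step 4: stage 0 rule, k = 8.** Both conditions must hold. At s = 0.3 the share is about 0% at a true 10 mg/g and 3% at a true 20 mg/g. At s = 0.5 it is 7% and 31%.

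**Step 5: unequal visit frequency.** Cox model, 3 years, doubling rule, s = 0.3 to 0.5, no treatment effect:

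- With no true progression at all, 4 against 2 visits a year gives a hazard ratio of about 1.5, and 4 against 1 gives 2.4 to 2.6.
- With true progression added (assumed log slope of mean 0.2 and SD 0.2 a year, s = 0.3), these fall to about 1.3 and 1.7. At 4 against 3 visits the ratio is about 1.1.
- With confirmation and no true progression, they are about 1.6 and 3. Far fewer events are false, but their dependence on visit frequency remains.

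**The case against.** **The protocol does not say that a single value is enough.** That is correct: it is silent, and an analysis plan not at hand could add confirmation. But the Synopsis does not defer the event definition. It writes out a rule for each stage, and those rules can be applied as they stand. A later plan that required confirmation would be changing the stated primary endpoint. The silence therefore limits how firmly the point can be put, but does not remove it.

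**A reader might infer that a large share of stable children in every stage would be miscounted.** The documents do not support that. Stage 0 needs both a level above 30 mg/g and a three-fold rise, and produces few false events unless the true level is near 30 mg/g and variability is high. In stage II with s = 0.2 the share is only 4% over 8 visits. The very high figures belong to stage I children close to 300 mg/g. Positively correlated errors would also lower all the shares.

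**A reader might infer that the treated-versus-untreated comparison is biased by a factor of 1.5 to 2.6.** That is not established either. Those ratios assume that no child truly progresses, in a disease the protocol describes as leading to renal failure early in life, and true progression dilutes them. They also assume a difference in visit frequency that the documents do not show. What stands is that nothing in the protocol prevents such a difference in a multi-country observational study, and that adjusting for covariates such as age does not correct for it.

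**Conclusion.** The point holds for progression from stage I and from stage II. As written, the first qualifying value at any routine consultation is the event. Under assumed within-child log SDs of 0.2 to 0.5 and 8 consultations, about 4% to 51% of stable stage II children and mid-range stage I children would be counted as progressed. At a true 200 mg/g the range is 18% to 79% (SD 0.2 to 0.4). The protocol gives neither the variability nor the number of visits, so the direction is secure and the size is not. It would be going too far to say that the primary endpoint mostly measures noise: that needs a variability and a rate of true progression that the documents do not give.

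The effect on the secondary comparison is conditional on unequal visit frequency. For the visit ratios examined and the unconfirmed rule, the null hazard ratios of 1.5 to 2.6 are an upper bound. This is an inexpensive improvement that should be made; it does not invalidate the study.

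**What to change.** 1. In the endpoint definition, count an albuminuria event only if the next documented value also meets the criterion, and date it at the first of the two. This matters for the stage I and stage II rules; applying it to stage 0 as well would keep the three rules parallel.
2. For the treated-versus-untreated comparison, use one value per common window in both groups, for example the value nearest each 6- or 12-month mark, at least as a sensitivity analysis. Confirmation alone does not remove the dependence on visit frequency.

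Averaging all available routine values before baseline looks like a natural third step but is not recommended in open-ended form. If albuminuria rose before baseline, the average is too low. With a prior rise of 0.2 to 0.3 log units a year and SD 0.3, confirmed false doubling was about 6.5% to 13.5%, against 5.0% with a single baseline value. If albuminuria fell after treatment started, the average is too high and events are suppressed, possibly only in treated children.

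The cost is wording and programming, with no new visits or samples. There will be fewer events. A qualifying value at a child's last visit cannot be confirmed, and the rule should say how it is handled. Values between windows go unused in the comparison.

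### The primary endpoint is named time to the next disease stage, but its II-to-III event is a doubling of albuminuria and shares no criterion with the protocol's own stage III

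*Protocol*

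**What the plan says.** The stage table (Protocol, section 5 Synopsis, Study Design) sets stage I at 30 to 300 mg albumin per g creatinine and stage II above 300 mg/g. Stage III is ">25% decline of normal creatinine clearance", and stage IV is end-stage renal failure.

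Under Study Objectives, the same synopsis names the primary endpoint as "time to progress of Alport Syndrome to the next disease stage under treatment" and lists three event rules labelled with the table's stage numbers:

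- For children who start in stage 0, two conditions must hold together: "Stage 0 to I : Albuminuria >30 mg albumin/gCrea in combination with a 3-fold increase from baseline in albuminuria".
- For children who start in stage I, either of two limbs is enough: "Stage I to II: Albuminuria >300 mg albumin/gCrea or two-fold increase from baseline albuminuria".
- For children who start in stage II, there is a single condition: "Stage II to III: Two-fold increase from baseline albuminuria".

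The secondary endpoint is "Time to progress of Alport Syndrome to the next disease stage under treatment compared to children without treatment".

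The table also governs entry. Children who were not in the EARLY PRO-TECT Alport trial must be in stage 0, I or II at baseline. Former participants are exempt from that limit. Kidney function is to be gathered from routine clinical records where they exist.

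**The concern.** A reader of the results will take time to the next stage to mean the stages the protocol has defined. For II-to-III it does not. The event requires no loss of clearance, and loss of clearance alone does not trigger it. Stage III therefore has two meanings in one study, one for eligibility and one for outcome. A new child at 800 mg/g with normal clearance is eligible as stage II, while a child who rises to that same state from 400 mg/g is recorded as having moved from II to III.

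A reported time to stage III could thus include children whose clearance is normal. Children who reach the table's two most advanced stages could appear as event-free. The study's hypothesis is that treatment slows disease progression, so the meaning of its progression endpoint matters. The treated-versus-untreated comparison rests on the same event.

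**Working it through.** The protocol gives no event rate, power or sample-size figure that bears on this point, so there is nothing to reproduce. The check applies the stage table and the event rules side by side.

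**Inputs.** Stage limits come from the table and event rules from the primary endpoint. Let b be baseline and v follow-up albuminuria in mg/g. Three readings are assumed: stage 0 means b < 30 (implied by the lower limit of stage I), a two-fold increase means v ≥ 2b, and a 3-fold increase means v ≥ 3b. The cases are illustrative and are not patient data.

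| Baseline stage | b → v | v/b | Clearance | Stage by table | Event by rule |
|---|---|---|---|---|---|
| II | 400 → 800 | 2.0 | normal | II | yes |
| II | 1000 → 1500 | 1.5 | 30% decline | III | no |
| II | 1000 → 1000 | 1.0 | 40% decline | III | no |
| II | 1000 → 1900 | 1.9 | renal failure | IV | no |
| I | 40 → 80 | 2.0 | normal | I | yes |
| I | 150 → 300 | 2.0 | normal | I | yes |
| I | 160 → 301 | 1.88 | normal | II | yes |
| 0 | 20 → 40 | 2.0 | normal | I | no |
| 0 | 20 → 60 | 3.0 | normal | I | yes |
| 0 | 5 → 31 | 6.2 | normal | I | yes |

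**II to III.** The rule is v ≥ 2b with no clearance or renal-failure term. The table's stage III has no albuminuria term. The two can disagree in both directions at every stage II baseline.

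**I to II.** Any v > 300 already counts under the first limb. The doubling limb acts alone only when 2b ≤ v ≤ 300, which needs b ≤ 300/2 = 150. With b ≥ 30 in stage I, the range is 30 to 150 mg/g. Every event added this way has v ≤ 300 and so is still stage I. Above 150 mg/g the 300 mg/g limit is crossed first, and the albuminuria boundary agrees with the table.

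**0 to I.** An entry into stage I is not counted when 30 < v < 3b, which needs b > 30/3 = 10. With b < 30 in stage 0, the range is above 10 and below 30 mg/g. At b = 20 the uncounted values lie above 30 and below 60. At or below 10 mg/g the 3-fold condition adds nothing once v exceeds 30.

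**Entrants at stage III or IV.** The rules stop at II-to-III. A former participant who enters at stage III has no event definition, and one who enters at stage IV has no further stage to reach.

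**The case against.** The strongest reply is that the three rules are printed beside the endpoint, so an analyst knows exactly what counts. Fold-rise conditions may be a deliberate guard against measurement noise, or albuminuria may be meant as a surrogate for progression. The population is in early disease and prospective follow-up runs at most from May 2021 to May 2024, so clearance loss and renal failure may be few. The stated aim of renal outcome is not limited to clearance or renal failure either.

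Much of this stands for the two lower transitions. The 0-to-I rule creates no false transition, because every event it counts has left stage 0. It is an openly stated stricter threshold, and it may delay an event rather than lose it: the child going from 20 to 40 mg/g counts on reaching 60. The doubling limb of I-to-II is explicit, and only its label is wrong. A reader might infer that all three rules are equally faulty, but the document does not support that.

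For II-to-III the reply fails. Nothing in the protocol calls the rule a surrogate or explains a departure from the table. Nor is this a detail left to an analysis plan, because the protocol itself fixes the events and such a plan would inherit the conflict.

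**Conclusion.** The protocol contradicts itself on its primary endpoint. The II-to-III event and the table's stage III share no criterion, so the plan as written labels some rises within stage II as stage III and does not register clearance loss or renal failure unless albuminuria also doubles. This holds at any stage II baseline and needs only the protocol's own text. It should be corrected before analysis. The I-to-II mismatch (baselines 30 to 150 mg/g) is a labelling fault. The 0-to-I mismatch (baselines above 10 and below 30 mg/g) calls for a clarification only. These limits rest on the readings of stage 0 and of fold increase stated with the check.

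The number of children affected cannot be computed, because the protocol gives no baseline albuminuria distribution and no progression or clearance-loss rates. A reader might infer that most events will be misclassified, or that the treated-versus-untreated comparison is biased in a particular direction. The document supports neither. Nor does this point say which definition of stage III is clinically right, only that the two must be reconciled.

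**What to change.** 1. Name the primary and secondary endpoints for what they measure: time to albuminuria-based progression, by baseline stage. Do not report fold-rises as stage transitions.
2. Add a separate named endpoint, time to stage III or IV, using the table's own clearance and renal-failure criteria and the kidney-function data already being collected.
3. State that the 3-fold condition for stage 0 children is stricter than the table's 30 mg/g boundary.
4. State how former EARLY PRO-TECT participants who enter at stage III or IV are handled, since no III-to-IV rule exists.

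Adding clearance loss and renal failure to the II-to-III event while keeping the present name would not be enough. It would change the primary event set, and rises such as 400 to 800 or 40 to 80 mg/g would still count in an endpoint named for stage transition.

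The cost is a text change and one further time-to-event analysis. The primary event set stays as it is, and no visits or tests are added. The downside is that kidney function comes from routine records as they happen to exist, and the protocol does not list creatinine clearance by name among the items collected. Stage III and IV events may therefore be detected late or missed. Keeping them in a separate endpoint keeps that irregularity out of the primary one.
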